## **AIMS:**

### **Aim 1. Acceptability, feasibility and safety of a yoga program for chronic pain in SCD.**

We will assess the acceptability of yoga for chronic pain in SCD. We will also assess the feasibility and safety of a yoga program for adolescents with SCD and chronic pain.

**Rationale:** Yoga content customized for patients with SCD chronic pain, is currently not available for patients. We propose for the first time to develop routines with consideration of needs, expectations and physical limitations of SCD. The overall acceptability, feasibility and safety of such a program in SCD is yet to be studied, though data from other chronic painful and inflammatory conditions do not suggest safety concerns.

**Hypotheses:** 1a) We hypothesize that more than >50% of those with chronic pain approached to complete a survey of their attitudes and practices related to yoga, would be willing to complete a survey. 1b) At least 50% of adolescent SCD patients with chronic pain offered participation in a yoga program through in-person yoga sessions will agree to participate in the yoga program 1c) At least 80% of participants enrolled in the in-person yoga program will be

able to attend at least 6 of 8 in-person yoga sessions. 1d) Fewer than 30% of participants will have an ED visit or hospitalization for pain within 24 hours of completion of a yoga session.

**Aim 2: Feasibility of collection of psychological and patient-reported outcomes in a study of yoga for chronic pain in SCD.**

**Rationale:** Yoga content tailored and customized for patients with SCD chronic pain, is currently not available for patients. We propose for the first time to develop routines with consideration of individual needs, expectations and physical limitations. In addition to aims in Aim 1, we propose to measure health outcomes and psychological characteristics pre- and post- the yoga program, with a goal to determine the feasibility of collection of these outcomes in a larger study. Since our sample size is small, and this is a pilot feasibility study, it will not be powered to assess measurable benefit (or lack of) from the yoga program, therefore these outcomes will be exploratory. These outcomes will be collected regardless of the number of yoga sessions attended.

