**Outcome Measures:**

**The study will have the following primary outcome measures:**

- 1- Proportion of adolescent patients with SCD and chronic pain approached that consent to participate in Part A.  
*The study hypothesis is that the proportion of adolescent patients with SCD and chronic pain approached that consent to complete a survey to assess attitudes and practices related to yoga (Part A) will be 50% or greater.*
- 2- Proportion of adolescent patients with SCD and chronic pain enrolled in Part A that consent to participate in Part B.  
*The study hypothesis is that the proportion of adolescent patients with SCD and chronic pain enrolled in Part A that consent to participate in Part B will be 50% or greater.*
- 3- Proportion of participants enrolled in Part B that attend at least 6 of 8 yoga sessions.  
*The study hypothesis is that the proportion of participants enrolled in Part B that attend at least 6 of 8 in-person yoga sessions will be 80 percent or greater.*
- 4- Proportion of participants enrolled in Part B with an ED visit or a hospitalization for pain within 24 hours of completion of each yoga session.

*The study hypothesis is that the proportion of participants enrolled in Part B with an ED visit or a hospitalization for pain within 24 hours of completion of each yoga session will be 30% or less.*

- 5- Proportion of participants in Part B who complete all study assessments.  
*The study hypothesis is that the proportion of participants who complete all study assessments before, and at the end of the yoga program will be 70% or greater.*
- 6- Adherence to submission of pain diary.  
*The study hypothesis is that the proportion of participants who submit at least 4 days of pain diary data before, and at the end of the yoga program will be 70% or greater.*

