#### **In-person yoga sessions:**

Patients will be offered a yoga program consisting of 8 in-person instructor-led group yoga sessions. Yoga sessions are likely to be held at CHOA campuses or at ECC, depending on availability of space. Based on number of participants enrolled and participant convenience/logistical issues, study cohort may be split into 2 or more groups, but a participant may only attend a total of 8 sessions. Sessions are currently planned to be weekly, however there may be variations in schedule to accommodate situations including but not limited to major holidays, school breaks, instructor illness, etc.

- i. During the sessions, participants will be monitored by a study investigator and the yoga instructor. An investigator who is an MD familiar with care of SCD patients will be present, and a RN may also be present, both of whom will monitor patient safety at each session.
- ii. Yoga instructor is certified and have expertise in teaching yoga. Instructor will be [name]. A physical therapist ([name]), who is also a certified yoga instructor, will also assist in developing the class routine, and may be present during the session.
- iii. The yoga instructors, with the guidance of SCD clinical experts, will develop a customized set of restorative yoga poses, breathing exercises, and guided relaxation routines with consideration of needs, expectations and physical limitations of SCD.
- iv. During guided yoga sessions the yoga instructor will carefully observe the participants for any sign of discomfort or suitability. Yoga instructors will modify particular poses to be suitable for the participant. The yoga sessions will be geared towards increased incorporation of breathing techniques and mindfulness and some 'asanas' (poses). Props may be utilized for yoga poses.
- v. Timing of yoga sessions will likely be in the evenings or on weekends, to accommodate participant's ability to attend these sessions. Participants will be asked regarding their preferred times. Every effort will be made to accommodate participants.

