#### **Total number of participants:**

*Part A, Group 1: Up to 40 adolescent patients who meet inclusion/do not meet exclusion criteria. Patient participants will be enrolled on Part A (up to a max of 40 patient participants) until 20 patient participants enroll on Part B.*

*Part A, Group 2: Up to 40 parents/guardians of adolescent patients in Group 1. The number of Group 2 participants will be determined by the number of Group 1 participants. Only one parent/guardian per Group 1 participant will be enrolled.*

*Part B, We anticipate enrolling up to 20 patients in Part B of the study.*

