#### **Monitoring of Potential adverse outcomes:**

**Pain:** There is a potential for increased discomfort and/or pain as a result of the yoga poses, even though the program is designed to be gentle. The potential for increased pain will be discussed with the participant during the consenting session and if needed, prior to each in-person yoga session, so the patient and their family are fully informed of the potential risks. Pain may result in increased use of medication, or potentially a ED visit, or hospitalization. We will also track healthcare utilization for pain, and if  $\geq 30\%$  of participants present with increased pain resulting in an ED visit or hospitalization, we will halt yoga sessions and reassess if any changes need to be made to the protocol. Since participants have chronic pain, it may be difficult to determine if the yoga program was the cause of increased pain, so we will go by patient self-report to determine if yoga program was believed to be causative. If this is the case, the participant may opt to discontinue the research study or a physician researcher may opt to withdraw the participant. We also anticipate that those who perceive an increase in pain following the program will self-discontinue from the study. Monitoring during yoga sessions will make every effort to ensure participants do not exceed their limitations.

**Other risks:** There is a possibility of muscle strain, of aggravation of an existing injury, which may cause discomfort or pain, increased medication use, need for medical treatment, increased time off work or school, or financial loss.

As with all research studies, there is also a risk of loss of confidentiality of participant data.

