#### *Data and Safety Monitoring Plan*

Research staff directly involved in the study will have access to data collected during this study. Paper documents will be filed in a locked filing cabinet in a secure office setting. Electronic data will be maintained on a secure Hematology/Oncology share-drive with limited access behind a secure firewall at Emory University or at CHOA. Participant data will be identified with a unique number. The key connecting the participant to the ID number will be maintained separately from the study data and will be destroyed upon completion of the study, to include dissemination of findings. The ID key will be accessible only to members of the research team. All audio recordings will be identified on the recording with the unique participant identification number. All transcripts will be identified using the participant identification number and names of parents and health care providers will be indicated with "XXX" in the transcription.

The data and safety monitoring team will include the Principal Investigator, co-Investigators and the study coordinator. Meetings will occur every 2 weeks from time of first yoga session, until 2 weeks after completion of the last yoga session. Investigators will discuss any concerns with yoga protocols utilized and if any modifications are needed for patient safety. All study data reviewed and discussed during these meetings will be kept confidential. Any breach in confidentiality will be reported to the IRB and regulatory agencies.

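### The primary safety criterion is strictly below 30% in hypothesis 1d but at most 30% in primary outcome 4, so 6 of 20 participants gives opposite verdicts (minor)

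*Combined protocol and SAP*

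**What the plan says.** Under Aim 1, hypothesis 1d reads: "Fewer than 30% of participants will have an ED visit or hospitalization for pain within 24 hours of completion of a yoga session". That is a strict inequality.

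Under Outcome Measures, primary outcome 4 is the "Proportion of participants enrolled in Part B with an ED visit or a hospitalization for pain" in the same 24-hour window. Its hypothesis is that this proportion "with an ED visit or a hospitalization for pain within 24 hours of completion of each yoga session will be 30% or less". That is an inclusive inequality. The counting unit is also worded differently: 1d speaks of *a* session, outcome 4 of *each* session.

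Under Total number of participants, Part A recruits, to a maximum of 40 patients, "until 20 patient participants enroll on Part B". Part B is described as up to 20.

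Under Monitoring of Potential adverse outcomes, if at least 30% "of participants present with increased pain resulting in an ED visit or hospitalization, we will halt yoga sessions and reassess". The rule gives no 24-hour window and no denominator.

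Analytic Methods plans descriptive statistics for Part B. It repeats no safety threshold and does not say which of the two versions governs.

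**The concern.** Outcome 4 is the only safety outcome among the six primary outcomes. With no formal test planned, the pre-stated threshold is the whole basis for saying whether the safety hypothesis was met. If two thresholds are in force and the result falls between them, the verdict can be chosen after the count is known. That matters only if the gap contains a count that the study can actually produce, so the check is whether one exists at the planned size and how likely it is.

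**Working it through.** **Inputs.** The two criteria (below 30%; at most 30%) come from hypothesis 1d and primary outcome 4. The Part B size of up to 20 comes from Total number of participants, and the denominator, participants enrolled in Part B, from outcome 4. The plan gives no sample-size or error calculation for this criterion, so there is no figure to reproduce. It gives no event rate either. R, the true risk that a participant has at least one qualifying event over the 8 sessions, is therefore an assumption, shown from 10% to 50%.

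**Step 1: where the criteria differ.** They differ only when x/n = 3/10 exactly, that is, when x = 3n/10 is a whole number. For n up to 20 this needs n = 10 (x = 3) or n = 20 (x = 6). At every other size they always agree.

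**Step 2: the verdicts around the boundary at n = 20.**

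| Participants with an event | Proportion | Hypothesis 1d (<30%) | Outcome 4 (≤30%) |
|---|---|---|---|
| 5 | 25% | met | met |
| 6 | 30% | not met | met |
| 7 | 35% | not met | not met |

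**Step 3: how likely the boundary count is.** Take X ~ Binomial(20, R), counting a participant with an event after any session, all sessions delivered, and participants independent with equal risk. Then P(X = 6) = C(20,6) R^6 (1 − R)^14, with C(20,6) = 38,760. At R = 0.30 this is 38,760 × 0.30^6 × 0.70^14 = 0.192. The chance of meeting the hypothesis is P(X ≤ 6) under outcome 4 and P(X ≤ 5) under 1d, and the difference is P(X = 6).

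| Assumed R | P(X = 6) | Met under outcome 4 | Met under 1d |
|---|---|---|---|
| 10% | 0.009 | 0.998 | 0.989 |
| 20% | 0.109 | 0.913 | 0.804 |
| 30% | 0.192 | 0.608 | 0.416 |
| 40% | 0.124 | 0.250 | 0.126 |
| 50% | 0.037 | 0.058 | 0.021 |

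**Step 4: the counting unit.** If outcome 4 is instead judged separately after each session, the per-session risk is q = 1 − (1 − R)^(1/8), which is 1 − 0.70^(1/8) = 0.044 at R = 0.30. The chance that at least one of the 8 sessions reaches 6 or more of 20 is 1 − [1 − P(Bin(20, q) ≥ 6)]^8. This is 0.0013 at R = 0.30 and 0.036 at R = 0.50. On that reading the criterion would almost never be failed at these risks, so *each* versus *a* session can matter more than the inequality sign and has to be settled with it.

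**The case against.** The strongest reply is that the discrepancy touches a single count. Twenty is a cap. With Part A limited to 40, reaching it needs at least 20/40 = 50% of Part A to enrol, which is itself the hypothesis under primary outcome 2. At any Part B size from 11 to 19 there is no conflict. A descriptive report would show 6/20 (30%) under either wording, so no data are lost. Hypothesis 1a and outcome 1 differ in the same way at 50%, which points to loose drafting rather than a considered choice. All of this stands, and it is why the point is minor. It does not remove the contradiction, because recruitment is aimed at exactly the size where it applies.

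A reader might go further and infer that the plan can halt the program for harm and still declare it safe, since the monitoring section stops sessions at 30% or more. The documents do not establish that. The halt has no stated window or denominator and may be meant more broadly than outcome 4. The nearby statement that "we will go by patient self-report to determine if yoga program was believed to be causative" may or may not limit which visits count, since the sentence after it concerns individual withdrawal. The halt is also a pause to reassess the protocol, not a finding that yoga is unsafe, and a precautionary trigger need not be the exact complement of an outcome threshold.

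A reader might likewise argue that the count would tend to freeze at 6 once sessions stop, making the overlap much more common than the figures above. That requires sessions never to resume. The plan says only that they halt while changes are considered, which points if anything towards resumption.

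**Conclusion.** The inconsistency is real and sits in current text. At the target size of 20, a count of 6 meets the safety hypothesis as written under outcome 4 and fails it as written under 1d, and nothing in the plan says which prevails. The chance of landing there is at most about 19% over the risks examined, and about 1% if the true risk is 10%. Those figures rest on an assumed risk, 20 enrolled, independent participants with equal risk, all sessions delivered, and an event after any session counting.

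If the monitoring halt does count the same events over the same participants, 6 of 20 would also trigger the pause. That is a supporting reason to prefer the strict wording, not a separate error. Severity: minor. It is a wording inconsistency in a decision threshold, with no effect on any test or on the data collected.

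**What to change.** Reword the hypothesis under primary outcome 4 so that the proportion of Part B enrollees with a pain-related ED visit or hospitalization within 24 hours after *any* yoga session is *less than* 30%. Both changes are needed. Changing the inequality alone would leave *each* session in outcome 4 against *a* session in 1d, and the two could still be computed differently. Keep the denominator that outcome 4 already states. At n = 20 the hypothesis is then met at 5 or fewer and not met at 6 or more.

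The edit is a few words and needs no new data. The cost is that 6 of 20 no longer passes. With all sessions delivered, the chance of meeting the hypothesis falls from 99.8% to 98.9% at a true risk of 10%, from 91% to 80% at 20%, and from 61% to 42% at 30%. If only 10 enrol, it falls from 88% to 68% at 20%.

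Aligning the other way, with 1d at 30% or less and the halt moved to above 30%, would also be consistent but is less protective. If the halt counts the same events, then at a true risk of 30% its count would be reached in 39% of trials (7 or more: 1 − 0.608) rather than 58% (6 or more: 1 − 0.416).

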**The study will have the following exploratory outcome measures (Change from baseline to end of yoga program):**

- 1- Chronic Pain Acceptance (Measured using the chronic pain acceptance questionnaire)
- 2- Fear of Movement (Measured using the Tampa Scale of Kinesiophobia)
- 3- Pain Intensity (Measured using PROMIS Pain Intensity Short Form)
- 4- Pain Interference (Measured using PROMIS Pain Interference Short Form)
- 5- Pain Catastrophizing (Measured using the Pain Catastrophizing Scale)
- 6- Expectations from the yoga program (Measured using the Modified EXPECT questionnaire)

## STUDY DESIGN

This study will be a 2-part study.

In Part A, there will be 2 groups of participants enrolled.

---Group 1 will include patients with SCD who meet inclusion criteria for the study, and do not have any exclusion criteria.

---Group 2 will include parents/guardians of patients who are in Group 1. Only one parent/guardian per participant will be enrolled.

Potential patient participants (Group 1) and their parent/guardian (Group 2) will be approached for participation in a survey based study to determine their attitudes and practices relating to yoga, and potential acceptability of a yoga based program for chronic SCD pain. They will complete the surveys as described in Part A as well as the demographics as detailed below. Medical records will be reviewed as described below for all participants in Group 1, but we will not review medical records of participants in Group 2. Both groups will separately consent to participation in the study. Parents/Guardians (Group 2) will be offered participation in Part A even if their child is 18 and older, as long as their child are enrolled in the study.

Patients in Part A Group 1 who indicate and interest and willingness to participate in a study of yoga for SCD pain will be offered Part B of the study, which will determine the feasibility and safety of a customized yoga program for SCD. The participant in Part A Group 1 does not have any commitment to enroll on Part B of the study, and does not necessarily have to express interest in participating in Part B of the study prior to participation in Part A. Participants in Group 2 will not be offered participation in Part B of the study.

**PART A: Assessment of attitudes and practices related to yoga and potential acceptability of a yoga program in adolescents with SCD and chronic pain, and their parents/guardians.**

**Inclusion Criteria for Group 1 participants:**

- 1-SCD, any genotype
- 2-Presence of chronic pain, the presence of chronic pain will be defined based on the frequency characteristic of the AAPT criteria for chronic SCD pain, as the presence of SCD-related pain on 15 or more days of the month for the past 6 months.
- 3-Age 12-21 at time of enrollment
- 4- English speaking

**Exclusion Criteria for Group 1 participants:**

- 1- Daytime or nighttime oxygen requirement for hypoxia
- 2- Most Recent Hemoglobin< 5 or platelet count < 20
- 3- Known Pregnancy
- 4- Severe cognitive issues not allowing for understanding consent/assent and instructions
- 5-History of overt stroke with significant residual motor weakness
- 6-History of recurrent syncope
- 7- Any other comorbidities or health concerns that the treating healthcare provider or investigators feel are a contra-indication for participation in the study.

**Inclusion/Exclusion Criteria for Group 2 participants:** There are no specific inclusion/exclusion criteria for parent/guardian participants, except that their child is a participant in the study.

We have developed a survey (attached-Survey Part A) to determine attitudes and practices relating to yoga in patients with SCD chronic pain, and potential acceptability of a yoga program for chronic SCD pain. The presence of chronic pain will be defined based on the based on the frequency characteristic of the AAPT criteria for chronic SCD pain, as the presence of pain on 15 or more days of the month for the past 6 months, and will be determined by self/parent report.

We will also collect the following questionnaires from Group 1 participants in the study: 1) Chronic pain acceptance questionnaire 2) Tampa Scale of Kinesiophobia 3) PROMIS Pain Intensity and Pain interference 4) Pain catastrophizing scale (Crombez et. al.). Surveys may be completed in person, or over the telephone, or may be mailed to participants to complete.

Medical records will be reviewed for pertinent demographic and clinical details including but not limited to those pertaining to SCD, healthcare utilization for pain, other pertinent details about pain phenotype, presence of fixed damage such as AVN, SCD complications, pertinent medical complications, medications, transfusions, and pertinent laboratory values such as (but not limited to) hematological parameters and markers of hemolysis. Since psychological diagnosis are often associated with chronic pain, we will review available psychological and mental health records for co-existing psychological diagnoses. Medical records will also be reviewed for inclusion and exclusion criteria. Note: Only medical records of patient participants (Group 1) will be reviewed; medical records of parent participants (Group 2) will not be reviewed.

We will also obtain demographic information including but not limited to age, sex, race, ethnicity, family income, insurance status, parent and child education status, family composition and parent marital status, religious affiliation, availability of transportation and distance from the

proposed yoga site. If participants indicate they have previously practiced yoga, we will also gather the following: when yoga was first practiced, number of months/years' yoga has been practiced, frequency of practice and time of most recent practice of yoga. For Group 1 participants, this form may be completed by the parent/guardian for those <18, and by the participant if >18, with or without assistance from the research coordinator. For Group 2 (parent) participants, this will be completed by the parent themselves, with or without assistance from the research coordinator.

At the end of Part A, Group 1 participants will be asked if they are interested in learning about participating a study of yoga for chronic SCD pain. If they answer yes, then they will learn more about the proposed program, and Part B of the study will be offered to them. In addition to the research coordinator discussing the Part B yoga program, we will use written materials to help participants become familiar with what they may expect in part B (attached with this protocol), which will include pictures of sample yoga and breathing routines. Participants may take the Part B consent form with them to think over if they wish to consider this prior to enrolling or refusing participation in Part B. If participants are not interested in a pilot study of yoga or do not wish to enroll/are unable to enroll on Part B, investigators will request and document reason for refusal (if provided), and participant will not have to complete additional study procedures. The proportion of those who complete Part A but do not wish to consent for Part B will be recorded. Group 2 participants will not be offered Part B.

It is anticipated that this introduction and pictures for part B will take approximately 10-15 minutes.

